
 To determine whether IM administration of Engensis has positive effects on survival in ALS Participants 	
 Time to all-cause mortality compared to Placebo

 To evaluate Quality of Life improvement following Engensis injections in ALS Participants compared to Placebo 	
 Change from Baseline (Day 0) in Quality of Life (QoL) using the ALS Assessment Questionnaire (ALSAQ; with 40 items, ALSAQ 40) on Day 365 for Engensis compared to Placebo

 To evaluate Patient and Clinical Reported Outcome improvement following Engensis injections in ALS Participants compared to Placebo 	
 Patient Global Impression of Change (PGIC) and Clinical Global Impression of Change (CGIC) at Day 365 for Engensis compared to Placebo

Overall Design

VMALS-002-02b is a Phase 2a, 6-month extension study, multicenter study designed to assess the long-term safety of Engensis (containing the active pharmaceutical ingredient VM202) in Participants with ALS.

Participants will be enrolled in the VMALS-002-2b study following the completion of the Day 180 Visit of Study VMALS-002-2. Participants will continue to be identified by the same Participant number.

Assessments to be conducted during this VMALS-002-2b extension study are as follows: vital signs; weight and height; complete physical examination; a record of all concomitant medications and procedures; ALSFRS-R; Handheld Dynamometry (HHD); Slow Vital Capacity (SVC); Amyotrophic Lateral Sclerosis Assessment Questionnaire, 40 questions (ALSAQ-40); Patient Global Impression of Change (PGIC); Clinical Global Impression of Change (CGIC); and urine pregnancy test for females of childbearing potential. Assessments of TEAEs, TESAEs, AESIs, and clinically significant laboratory values will continue from the Day 180 Visit of Study VMALS-002-2 throughout the VMALS-002-2b extension study, to Day 365.

Study and Treatment Duration:

There will be no treatments during this extension study. The timing for visits in the VMALS-002-2b study starts at the conclusion of the Day 180 Visit in VMALS-002-2. Participants in VMALS-002-2b will be followed for 180 days to Day 365.

Visit Frequency:

Consented Participants will be seen and evaluated for safety at visits every 60 days (Days 240, 300, and 365/ET).

Intervention Groups and Duration:

[figure not shown]

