3.2 Exploratory Endpoints

- Change from Baseline (Study VMALS-002-2 Day 0) in total mean Revised Amyotrophic Lateral Sclerosis Function Rating (ALSFRS-R) scores at Day 365 for Engensis compared to Placebo
- Change from Baseline (Study VMALS-002-2 Day 0) in ALSFRS-R subscores for Fine and Gross Motor Functions (sum of scores for items 4 to 9) and for Bulbar Function (sum of scores for items 1 to 3) at Day 365 for Engensis compared to Placebo
- Changes in the slope of the total ALSFRS-R score over time for Engensis compared to Placebo
- Change from Baseline (Study VMALS-002-2 Day 0) in muscle strength assessed bilaterally by Handheld Dynamometry (HHD) in muscles in the upper and lower extremities at Day 365 for Engensis compared to Placebo
- Change from Baseline (Study VMALS-002-2 Day 0) in Quality of Life (QoL) using the ALS Assessment Questionnaire (ALSAQ; with 40 items, ALSAQ 40) on Day 365 for Engensis compared to Placebo
- Patient Global Impression of Change (PGIC) and Clinical Global Impression of Change (CGIC) at Day 365 for Engensis compared to Placebo
- Change from Baseline (Study VMALS-002-2 Day 0) in Slow Vital Capacity (SVC) at Day 365 for Engensis compared to Placebo
- Time to tracheostomy for Engensis
- Time to all-cause mortality compared to Placebo

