6.2.3 Duration / Study Day / Time

Study day will be calculated as the number of days from first Study Injection in the Study VMALS-002-2:

- date of event – date of first Study Injection + 1, for events on or after first Study Injection in the Study VMALS-002-2
- date of event – date of first Study Injection, for events before first Study Injection in the Study VMALS-002-2

Duration of ALS diagnosis will be presented in months and calculated as (Date of Screening of the Study VMALS-002-2 – Date of Onset of Symptoms +1) / 30.4375.

QMD Ref: Worldwide-TMP-ST-005-7.0 Effective: 12Aug2019	Governing QMD: Worldwide-SOP-ST-001
Confidentiality Statement	

This document is the property of Worldwide Clinical Trials Inc. and may not be duplicated, copied, altered or removed from company without prior approval from Worldwide Quality Assurance or in compliance with Worldwide Standard Operating Procedures.

Worldwide Clinical Trials Controlled Quality Management Document			
 WORLDWIDE CLINICAL TRIALS	Sponsor:	Helixmith Co., Ltd.	
	Protocol Number:	VMALS-002-2b	
STATISTICAL ANALYSIS PLAN. PHASE 2-3-4			

Time to tracheostomy will be calculated as time from date of first Study Injection in the VMALS-002-2 Study to date of first occurrence of ALSFRS-R questionnaire with answer “**0 - Invasive mechanical ventilation by intubation or tracheostomy**” to question “**12. Respiratory insufficiency**” (ASLFRS-R date – date of the first injection +1) presented in days.

Time to all-cause mortality will be calculated as the time period from date of first Study Drug Injection in the Study VMALS-002-2 to date of death within 365 days presented in days (death date – date of the first injection +1).

Both time-to-event endpoints will be censored by date of last visit.

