6.15 Exploratory Analyses

6.15.1 Revised Amyotrophic Lateral Sclerosis Functional Rating Scale (ALSFRS-R)

ALSFRS-R will be measured at Day 240, Day 300 and Day 365. Total score and subscores for Fine and Gross Motor Functions (sum of scores for items 4 to 9) and for Bulbar Function (sum of scores for items 1 to 3) their changes from baseline will be presented with descriptive statistics by visits and treatment group (Table 14.6.1, Listing 16.2.9.1).

Slope of the total score will be provided using graphical presentation of values by visit for both treatment group. The figures will be presented using time points from both VMALS-002-2 and VMALS-002-2b studies.

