6.15.6 Time to tracheostomy

Time to tracheostomy will be presented with descriptive statistics and corresponding survival curves using Kaplan- Meier analysis (Table 14.6.8, Listing 16.2.9.8).

SAS code example for Kaplan-Meier analysis:

```
proc lifetest data=DATAIN method = km;
  time AVAL*CNSR(1);
  strata TRT01PN / test = logrank;
run;
```

DATAIN – source dataset

AVAL – time to event

CNSR – flag for censoring, if CNSR=1 then the corresponding value of AVAL is a censored value and not an observed event

TRT01PN – treatment group

Analysis will be performed on data combined for core study the Study VMALS-002-2 (Screening, Day 0 pre-dose, Day 30, Day 60 pre-dose, Day 84, Day 120 pre-dose, Day 144 and Day 180) and for this extension study the Study VMALS-002-2b (Day 240, Day 300, Day 365/ET4).

QMD Ref: Worldwide-TMP-ST-005-7.0 Effective: 12Aug2019	Governing QMD: Worldwide-SOP-ST-001
Confidentiality Statement	

This document is the property of Worldwide Clinical Trials Inc. and may not be duplicated, copied, altered or removed from company without prior approval from Worldwide Quality Assurance or in compliance with Worldwide Standard Operating Procedures.

Worldwide Clinical Trials Controlled Quality Management Document			
 WORLDWIDE CLINICAL TRIALS	Sponsor:	Helixmith Co., Ltd.	
	Protocol Number:	VMALS-002-2b	
STATISTICAL ANALYSIS PLAN. PHASE 2-3-4			

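### The ALSFRS-R slope endpoint is delivered only as a figure of values by visit, with no time scale and no slope per unit time; on equally spaced visits a constant decline could look about 2.1 times steeper after Day 180

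*SAP*

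**What the plan says.** SAP 3.2 lists the endpoint as "Changes in the slope of the total ALSFRS-R score over time for Engensis compared to Placebo"; the protocol's objectives tables (Sections 1.1 and 3) carry the same endpoint. The only analysis named for it is in SAP 6.15.1: "Slope of the total score will be provided using graphical presentation of values by visit for both treatment group". The next sentence extends the figure over both studies: "The figures will be presented using time points from both VMALS-002-2 and VMALS-002-2b studies". Table 14.6.1 gives scores and changes from baseline by visit, but no slope.

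For the extension, SAP 6.15.1 states "ALSFRS-R will be measured at Day 240, Day 300 and Day 365", which agrees with the protocol's schedule of activities. The documents supplied do not state the ALSFRS-R schedule of the core study. The nearest source is SAP 6.15.6 (time to tracheostomy), which gives the core visits as "Screening, Day 0 pre-dose, Day 30, Day 60 pre-dose, Day 84, Day 120 pre-dose, Day 144 and Day 180". SAP 6.2.3 derives that event from item 12 of the scale, as the "date of first occurrence of ALSFRS-R questionnaire with answer" meaning invasive ventilation or tracheostomy.

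SAP 6.2.3 also derives study day from the first injection. SAP 6.2.13 merges early termination data with Day 365 in the tables and does not mention figures.

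**The concern.** A slope has meaning only against a time axis. Here the reader must judge it by eye from a figure whose axis is described only as visit. Visit spacing appears to change at Day 180, where the core study ends and the extension begins. If visits are drawn at equal distances, each extension step covers about twice as much time as a core step, and the line bends there even when the true rate is constant.

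What is at stake is the reading of each arm's course after Day 180. A steady decline could be read as acceleration, and a real slowing could go unseen. With at most 18 participants and no numerical slope, the figure is the whole result for this endpoint.

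**Working it through.** The documents state no slope, rate or power figure for this endpoint, so there is nothing to reproduce. The check is how a known decline would look on each kind of axis.

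**Inputs**
- Core visit days (SAP 6.15.6): 0, 30, 60, 84, 120, 144, 180. Screening has no stated day and is left out. Treating these as ALSFRS-R visits is an inference.
- Extension visit days (SAP 6.15.1): 240, 300, 365, starting from Day 180.
- Rate of decline: an assumption, 1 point per 30 days. Any constant rate cancels in the ratio.

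**Gaps**
- Core: 30, 30, 24, 36, 24, 36 days; mean 180/6 = 30.0.
- Extension: 60, 60, 65 days; mean 185/3 = 61.7.
- Ratio of means: 61.7/30.0 = 2.06. Single-gap ratios run from 60/36 = 1.67 to 65/24 = 2.71.

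**Constant decline on equally spaced visits** (least-squares slope on visit number, in points lost per visit)
- Core: points lost are 0, 1, 2, 2.8, 4, 4.8, 6. With visit number centred at -3 to 3, the slope is (-2 - 2 + 0 + 4 + 9.6 + 18)/28 = 27.6/28 = 0.986.
- Extension, from Day 180: points lost are 6, 8, 10, 12.17. With visit number centred at -1.5 to 1.5, the slope is (-9 - 4 + 5 + 18.25)/5 = 10.25/5 = 2.05.
- Apparent steepening: 2.05/0.986 = 2.08. Runs at 0.5, 1.0 and 1.5 points per month all gave 2.08.

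**True 50% slowing after Day 180, same axis**
- Further points lost from Day 180: 0, 1, 2, 3.08. The slope is (0 - 0.5 + 1 + 4.625)/5 = 5.125/5 = 1.025 per visit, against 0.986 before. The halving of the rate cannot be seen.

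**Constant decline on an axis in days**
- The slope is the same before and after Day 180: ratio 1.00.

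**Sensitivity to the inferred core schedule**
- If ALSFRS-R had been done only at Days 0, 60, 120 and 180, the mean core gap would be 60 days and the ratio of mean gaps 61.7/60 = 1.03, which is almost no distortion at the changeover.

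**The case against.** The strongest reply is that the artefact is possible but not planned. The SAP does not say that visits are equally spaced. Visits are named by day number, and a by-visit figure can place Day 240 at 240, in which case nothing bends. SAP Section 11, which lists the figures, is not readable in the public copy, so the layout cannot be checked. This stands, and it makes the factor of 2.1 conditional. It does not supply a slope per unit time, and the methods text still leaves the axis open. The core schedule is likewise inferred, and the sensitivity result above shows how much depends on it.

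Second, the endpoint compares arms, and both arms share the visits. This also stands: an equally spaced axis cannot turn equal arms into different ones. It could only make an existing slope difference seem to widen faster per visit after Day 180.

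Third, the endpoint is exploratory and descriptive, and Table 14.6.1 and Listing 16.2.9.1 let a reader recover the values. That limits the consequence, but neither is described as giving a slope.

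A reader might go further and infer two things that the documents do not support:
- **That the bend would fall where dosing ends.** The last core visit labelled pre-dose is Day 120, and the listed gaps stay at 24 and 36 days from there to Day 180. The full core dosing schedule is not in these documents. What changes at Day 180 is the study, and with it the visit spacing.
- **That the figure would imitate the course described for the earlier ALS study, VMALS-001.** There the plateau or slowing was reported up to Day 90 and was lost afterwards. The possible bend here is at Day 180, so the two do not match.

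**Conclusion.** The point holds in conditional form. It is certain that an endpoint defined over time has, as its only stated analysis, a figure of values by visit across two studies, with no time-scaled axis stated in the methods text and no slope per unit time. Two conditions decide the size of any distortion: that ALSFRS-R was done at the core visits listed for the tracheostomy analysis, and that visits are spaced equally on the axis. If both hold, a constant decline looks about 2.1 times steeper after Day 180 and a 50% slowing is hidden. If the axis is already scaled in days there is no distortion, and if the core assessments were 60 days apart there is almost none at the changeover. The damage is to reading change within an arm. The change is still worth making, because it removes the ambiguity and lets the trial report the slope it names as an endpoint.

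**What to change.** In SAP 6.15.1, replace the by-visit figure with a plot of total score on a linear axis in days:
- arm means at the nominal visit day, since visits have a window of ±7 days;
- individual profiles, including early termination values, at actual study day as derived in SAP 6.2.3, so that the tables' merging of early termination with Day 365 is not carried into the figure.

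SAP 6.2.3 counts the day of first injection as day 1, so subtract one where study day and nominal visit day share the axis.

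Add one small table giving, by arm, the mean change in points per 30 days for Day 0-180 and for Day 180-365. For each participant and period this is 30 × (last score - first score)/(actual days between them). Report it with the number contributing and descriptive statistics only.

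The cost is a few lines of SAP text, a little extra programming and one summary table. Study day is already derived, and no new data are needed.

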6.15.2 Handheld Dynamometry (HHD)

HHD will be measured at Day 240, Day 300 and Day 365. Maximal values of strength of each muscle group of 3 trials and their changes from baseline will be presented with descriptive statistics for each visit by treatment group (Table 14.6.2, Listing 16.2.9.2).

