2.2.6.1. Phase 1/2 Study in Participants with Amyotrophic Lateral Sclerosis

A Phase 1/2, open label, single center study in 18 Participants diagnosed with clinically definite, clinically probable, or clinically probable-laboratory supported ALS (VMALS-001; NCT02039401) lasting 9 months was completed.⁶¹ Prior to injections on Day 0, Participants were assessed using the ALSFRS-R, the Medical Research Council (MRC) scale for muscle strength testing, dynamometry, forced vital capacity (FVC), and muscle circumference of treated muscles.

All Participants (18 Participants) received a total of 64 mg of Engensis IM in the upper limbs (abductor pollicis brevis, first dorsal interosseous, biceps, deltoid, extensor carpi radialis, flexor carpi ulnaris, and flexor carpi radialis) and lower limbs (quadriceps, gastrocnemius, and tibialis anterior).

Engensis was administered over the course of four visits: Days 0, 7, 14, and 30. As in previous Engensis studies, the final dose of Engensis for each target muscle group was divided and administered 2 weeks apart with injection of the upper limbs at separate visits followed by injection of the lower limbs.

Post-injection, ALSFRS-R, FVC, and muscle strength (determined by the MRC scale) were assessed at Days 30, 60, and 90, and at 6 and 9 months. Muscle circumference and dynamometry were conducted on Days 60 and 90, and at 6 and 9 months. Participants were contacted through 36 months by phone to assess survival.

After Engensis or Placebo injections through Day 30, seventeen (17) Participants completed the 9-month follow-up; one Participant died prior to the 9-month visit. Three (3) Participants completed the study (36-month follow-up), while 14 Participants died following the 9-month visit; all deceased Participants died due to respiratory failure associated with ALS. Four additional serious adverse events (SAEs) that required hospitalization were reported. All deaths and SAEs were classified as unrelated to the study drug. Injection site reactions were limited to pain and/or bruising and none exceeded grade 2 severity.

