8.2.2. Handheld Dynamometry

Muscle strength will be measured quantitatively by HHD and the change from baseline (Day 0, VMALS-002-2) in HHD following Engensis injections as compared to Placebo. HHD is a procedure by which a dynamometer is applied to the body of an individual being tested.⁶⁴

A non-AC powered dynamometer (manufactured by Hoggan Health Industries, Inc) will be used at all clinical sites. These measurements will be performed on Days 240, 300, and 365/ET. Strength measurements will be evaluated for individual muscles.⁶⁵

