9.1. Sample Size Determination

The number of Participants in this study will be determined by the number who complete the Day 180 Visit in VMALS-002-2.

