4 SAMPLE SIZE

The number of Participants in this study will be determined by the number who complete the Day 180 Visit in VMALS-002-2. The maximum potential Participants in VMALS-002-2b is 18, based on enrollment in VMALS-002-2.

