6 PLANNED ANALYSES

No statistical analysis plan (SAP) prepared in advance of the data can be absolutely definitive and the final Clinical Study Report (CSR) may contain additional tables or statistical tests if warranted by the efficacy and safety data results. The justification for any such additional analyses will be fully documented in the final CSR.

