6.3 Conventions

All data listings, summaries, figures and statistical analyses will be generated using SAS version 9.4 or higher¹ unless otherwise noted.

Summaries will be presented by treatment group. Treatment group labels will be displayed as follows:

Engensis (N=XX)	Placebo (N=XX)	Overall (N=XX)
--------------------	-------------------	-------------------

Listings will be sorted in the following order treatment group, Participant, parameter unless otherwise stated. All data will be listed.

Continuous variables will be summarized by the number of non-missing observations, mean, median, standard deviation, and minimum and maximum. For all tabulations of changes from baseline data, the lower and upper 95% confidence limits for the mean for the individual treatments will be given.

Categorical variables will be summarized by presenting the frequency and percent. Percentages will be based on the number of non-missing observations or the participant population unless otherwise specified. For each variable, all categories will be shown. Zero frequencies (but not the percent) within a category will be presented.

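### Hand-held dynamometry is summarised only as raw per-muscle rows; one pre-specified standardised strength score would be a cheap improvement

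*SAP*

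**What the plan says.** The exploratory endpoint in SAP section 3.2 is change from Day 0 of the parent study in "muscle strength assessed bilaterally by Handheld Dynamometry (HHD) in muscles in the upper and lower extremities at Day 365 for Engensis compared to Placebo". The protocol objectives table words it the same way.

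Protocol section 8.2.2 sets the unit of evaluation: "Strength measurements will be evaluated for individual muscles". SAP section 6.15.2 follows it: "Maximal values of strength of each muscle group of 3 trials and their changes from baseline will be presented with descriptive statistics", for each visit and treatment group. The protocol speaks of muscles and the SAP of muscle groups. Neither names or counts them, and neither says how the two sides are combined.

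The derived-data rules in SAP section 6.2 contain no HHD score. They do define a total and subscores for the ALSFRS-R (6.2.9) and five subscales with missing-item rules for the ALSAQ-40 (6.2.10).

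For changes from baseline, SAP section 6.3 adds that "the lower and upper 95% confidence limits for the mean for the individual treatments will be given". That is a within-arm interval. SAP section 4 caps the sample: "The maximum potential Participants in VMALS-002-2b is 18, based on enrollment in VMALS-002-2".

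**The concern.** HHD is the only direct measure of muscle strength in the study, and the objective is about strength in the arms and legs, not about any one muscle. The plan yields a set of separate rows with none designated as the result. With at most 18 people, each row is imprecise.

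SAP section 6 also leaves room to add analyses once results are known: "the final Clinical Study Report (CSR) may contain additional tables or statistical tests if warranted by the efficacy and safety data results". The justification must be documented in the report, but with no summary named in advance, any single muscle can become the strength result. The protocol synopsis shows how naturally this happens. Its account of the earlier ALS study says the ALSFRS-R plateau was not seen after 90 days, then singles out bulbar and breathing functions as the exception.

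At stake are the precision available from data already being collected, and a single strength result fixed before the data are seen.

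**Working it through.** **Inputs.** The plan has no HHD figure to reproduce. Protocol section 9.1 says only: "The number of Participants in this study will be determined by the number who complete the Day 180 Visit in VMALS-002-2". It gives no power, effect or SD.

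- Maximum sample: 18 (SAP section 4).
- Number of muscles *k*: not given; assumed 4 to 20. The nearest list is of the muscles injected in VMALS-001 (protocol section 2.2.6.1), seven in the upper limb plus "quadriceps, gastrocnemius, and tibialis anterior", 10 in all. It is not an HHD list, so 10 serves only as an example.
- Correlation *r* between muscles in their change: not given; assumed 0.3 to 0.7.
- Arm split: not given; 9:9 assumed, with 12:6 as a check.
- Equal variances after standardising, and an effect common to all muscles: assumed.

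**Step 1: information in a composite.** The mean of *k* equally correlated muscles has variance σ²(1 + (*k* − 1)*r*)/*k*. Relative to one muscle, its information is *k*/(1 + (*k* − 1)*r*):

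| *k* | *r* = 0.3 | *r* = 0.5 | *r* = 0.7 |
|---|---|---|---|
| 4 | 2.11 | 1.60 | 1.29 |
| 10 | 2.70 | 1.82 | 1.37 |
| 20 | 2.99 | 1.90 | 1.40 |

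For example, 10/(1 + 9 × 0.5) = 10/5.5 = 1.82. One muscle then holds 5.5/10 = 55% of the composite's information, a loss of about 45% (44% if the ratio is rounded to 1.8).

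**Step 2: precision.** At 9:9, the 95% half-width for a difference in one muscle is 2.12 × √(2/9) = 1.00 SD. For the composite at *k* = 10 and *r* = 0.5 it is 1.00/√1.82 = 0.74 SD. Over the whole grid it runs from 1.00/√2.99 = 0.58 to 1.00/√1.29 = 0.88 SD.

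**Step 3: picking out one muscle.** With no true effect, the absolute arm difference in one muscle named in advance averages √(2/9) × √(2/π) = 0.471 × 0.798 = 0.38 SD. In a simulation (20,000 runs, 9:9), the largest of 10 such differences averaged 0.85, 0.80 and 0.72 SD at correlations 0.3, 0.5 and 0.7. That is about twice as large. At 12:6 the values were 0.91, 0.85 and 0.77.

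**Step 4: which scale.** Percent of own baseline is undefined at zero force and unstable near it. If 19 muscles stand at 70% of baseline and one goes from 2 to 5 units (250%), the mean is (19 × 70 + 250)/20 = 79%. One nearly powerless muscle has moved the score by 9 points. Dividing each muscle's change by an SD common to all participants avoids this.

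**The case against.** The strongest reply is that the per-muscle analysis is the pre-specified one. Protocol section 8.2.2 asks for individual muscles and the SAP delivers them. The endpoint speaks of strength in muscles, so a muscle-by-muscle table is a fair reading of it, and the endpoint fixes the visit at Day 365. Treatment was given by local intramuscular injection, which gives single-muscle results a rationale, and a composite can dilute a regional effect. All of this stands. It makes the point an improvement rather than a contradiction, and it is why the per-muscle rows should stay.

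Three stronger readings are tempting, and the documents do not support them.

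- A reader might infer an inflated false-positive rate. If each of 10 muscles were tested at 9:9, the chance of at least one nominal p < 0.05 under no effect would be 36%, 30% or 22% at correlations 0.3, 0.5 and 0.7. But the SAP plans no HHD test and no between-arm interval.
- A reader might take the ratio of 1.8 as a property of this trial. It needs a correlation near 0.5 and about 9 or 10 muscles, and neither is documented.
- A reader might infer that raw units let strong muscles dominate. That would apply to a raw sum or average; in separate rows no muscle outweighs another.

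Two limits remain. The SAP's list of tables is blacked out, so the layout of Table 14.6.2 cannot be checked. The parent study's HHD methods are also not in these documents. That there is no composite rests on the text of SAP sections 6.2 and 6.15.2.

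**Conclusion.** The point holds as a low-cost improvement to an exploratory endpoint. The visible plan has no overall or limb-level HHD score, no muscle list and no designated row, in a study of at most 18 people.

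Under the stated assumptions, a standardised composite carries about 1.3 to 3.0 times the information of one muscle. The gain shrinks if muscles change closely together or if the effect is confined to a few of them. Standardising by Day 0 SD puts muscles on a common scale but does not guarantee equal variances of change, so the ratios are approximate.

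The harm to guard against is selective emphasis on one row. The primary safety objective is not affected.

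**What to change.** In SAP section 6.15.2:

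1. List the muscles tested, with sides.
2. Derive one score per participant and visit. Take each muscle's best of three trials and standardise it by that muscle's Day 0 mean and SD, pooled over both arms. Average over sides and muscles for upper limb, lower limb and overall. The mean cancels in the change score, and the SD acts as a fixed weight that is the same for everyone.
3. Score a muscle that was tested but produced no force as zero force, not as missing. State the minimum number of muscles that must be measured at both Day 0 and the visit, and compute change over those muscles only.
4. Name the change in the overall score at Day 365 as the HHD summary result, with the between-arm difference and its 95% CI. Label the limb scores and per-muscle rows as supportive.
5. Record the addition in SAP section 9, which now states that there are no changes, because protocol section 8.2.2 specifies individual muscles.

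The cost is SAP wording, one derived variable and a few table rows, settled before database lock. It needs no new data or visits. The per-participant values are due in Listing 16.2.9.2 anyway, but a score built from them later would be post hoc. The one downside, dilution of a regional effect, is limited by keeping the limb scores and single muscles visible.
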